WW will see participant use data that is entered into the WW appVirtual Workshops and in the Facebook group. WW will also have participant contact information from the NDA (name, email, phone, and address) and the technical troubleshooting email communication. WW may also email participants materials pertaining to weekly topics in the Virtual Workshops or regarding the food plan. Participants sign up for the app using their email address. This is no different from the commercially available app or commercially available plans WW offers. Additionally, we will send them de-identified assessment data as well as project reports. There is a chance that they will be able to link the assessment data with the engagement data entered into WW app virtual workshops and the Facebook group through participants comments and weight entries.

Additionally, it is possible that participants in this study know each other.

If participants will be screened, describe the plans for storage or destruction of identifiable data for those that failed the screening.]

Contact information will be stored in a REDCap form with an indication that they are not eligible. However the data collected from the screening, including reason ineligible, will be stored in a separate form and will be de-identified at the end of the study.

Privacy/Confidentiality Part 2: Complete the Data Security Assessment

Form: [This form IS REQUIRED for ALL studies. The form is available here - <https://ovpr.uconn.edu/services/rics/irb/irb-forms-infoed/>. This form will be used to assess procedures for protecting confidentiality of data collected during the study and stored after closure. It will also be used to assess plans for storage and security of electronic data in accordance with University Best Practices. Review the document proving tips to complete the form located at <http://content.research.uconn.edu/pdf/storrs/rcc/TipsDataSecurityAssessmentForm.docx>.

Informed Consent

As PI, you are responsible for taking reasonable steps to assure that the participants in this study are fully informed about and understand the study. Even if you are not targeting participants from “Special Populations” as listed on page 4, such populations may be included in recruitment efforts. Please keep this in mind as you design the Consent Process and provide the information requested in this section.

Consent/permission Setting: [Describe the consent/permission process including *who* will obtain it, *where* and *when* will it be obtained, and *how* much time participants will have to make a decision. Describe how the privacy of the participants will be maintained throughout the consent process.

A signed consent waiver is being requested for this study. Participants will review an informational page before completing the initial survey screener. Ample time will be allowed for

discussion or questions. Consent will be reviewed during the telephone screening by research assistants/coordinators trained in the consent process.

State whether an assessment of consent/permission materials will be conducted to assure that participants understand the information (may be warranted in studies with complicated study procedures, those that require extensive time commitments or those that expose participants to greater than minimal risk).]

We will not perform an assessment to ensure participants understand the information, however we will conduct an interactive webinar to discuss any concerns or questions.

Capacity to Consent: [Describe how the capacity to consent will be assessed for participants with limited decision-making capacity, language barriers or hearing difficulty. If a participant is incapable of providing consent, you will need to obtain consent from the participant's legal guardian (please see the IRB website for additional information).]

To be able to actively participate in the study, participants must be adults without impaired decision making ability that are able to speak and read English. The consent process will include a discussion of the participants understanding of what participating in research means including their rights as a research participant, the protocol, as well as risks and potential benefits to participating in the study. If research personnel obtaining consent believes there is a concern regarding a participant understanding participation will be discussed with the program director who will determine whether to exclude the participants on this basis.

Parent/Guardian Permission and Assent: [If enrolling children, state how many parents/guardians will provide permission, when the child's assent will be obtained and if assent will be written or oral. Provide a copy of the script to be used if oral assent will be obtained. For longitudinal studies, assent may happen at several points during the study.]

N/A

Documentation of Consent: [Specify the forms that will be used for each participant population, i.e., adult consent form, surrogate consent form, parental permission sheet, child assent form (written form or oral script) or an information sheet. Copies of all forms should be attached to this application in the same format that they will be given to participants (templates and instructions are available on the IRB website).]

An information sheet will be used for the study participants.

Waiver or Alteration of Consent: [The IRB may waive or alter the elements of consent in some minimal risks studies. If you plan to request either a **waiver of consent** (i.e., participants will not be asked to give consent), an **alteration of consent** (e.g., deception) or a **waiver of signed consent** (i.e., participants will give consent after reading an information sheet), please answer the following questions using specific information from the study:]

Waiver (i.e. participants will not be asked to give consent) or alteration of consent (e.g. use of deception/incomplete disclosure in research):

- Why is the study considered to be minimal risk?

- How will the waiver affect the participants' rights and welfare? The IRB must find that participants' rights are not adversely affected. For example, participants may choose not to answer any questions they do not want to answer and they may stop their participation in the research at any time.
- Explain why the research could not be practicably carried out without the waiver. For studies that involve deception, explain how the research could not be done if participants know the full purpose of the study.
- Explain why the research could not be practicably carried out without using identifiable private information and/or identifiable biospecimens.
- How will important information be returned to the participants, if appropriate? For studies that involve deception, indicate that participants will be debriefed and that the researchers will be available in case participants have questions.
- Indicate if the waiver/alteration as noted above is applicable to the entire study or to a portion of the study.

Waiver of ***signed*** consent (i.e. , no signature, participants give consent only after reading an information sheet). Tip: if the investigator will obtain information through oral or written communication with the prospective participant or if the investigator will obtain private identifiable information or identifiable biospecimens by accessing records, then a waiver of signed consent is NOT required.:

We are requesting a waiver of signed consent to be able to recruit participants across the US for an online study.

- Why is the study considered to be minimal risk?

The study is minimal risk because includes surveys and a weight loss intervention.
The weight loss intervention is commercially available.

- Does a breach of confidentiality constitute the principal risk to participants? Relate this to the risks associated with a breach of confidentiality and indicate how risks will be minimized because of the waiver of signed consent.

The ability to review the consent online will limit any risks of travelling to the study site needed to complete an in-person consent.

- Would the signed consent form be the only record linking the participant to the research? Relate this to the procedures to protect privacy/confidentiality.

No. We also utilize contact information to communicate with participants throughout the study.

- Does the research include any activities that would require signed consent in a non-research setting? For example, in non-research settings, normally there is no requirement for written consent for completion of questionnaires.

No.

- Describe if the participants or their legally authorized representatives are members of a distinct cultural group or community in which signing forms is not the norm, the research presents no more than minimal risk of harm to subjects and there is an appropriate alternative

mechanism for documenting that informed consent was obtained. Not applicable to FDA Regulated Studies.
N/A

References / Literature Review:

1. Weight Watchers. About. <https://www.weightwatchers.com/us/>. Accessed 02/06/2020.

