1. To examine the preliminary outcomes and acceptability of a multicomponent online commercial weight loss program that includes a mobile app, weekly virtual workshops, and an online community. Preliminary outcome is defined as weight change from baseline to 3 and 6-months. Secondary preliminary outcomes include changes in diet quality, physical activity, quality of life, sleep quality, and food cravings from baseline to 6 months. Acceptability of each program component and the overall program will be evaluated at 6 months.
2. To examine whether greater app use, greater engagement in the online community, and engagement with a higher number of peers (in the online community) predict greater weight loss at 3- and 6-months.
3. To examine the associations between total use of program components (and each individual program component) and change in weight. We hypothesize that greater use of program components (individually and total) will predict greater weight loss.

For EACH Participant Population State the Number of Participants to be Enrolled and Screened and/or the number of participant records reviewed (including, HIPAA covered health records and FERPA covered school records), if applicable: [State the total number of participants/records to be enrolled and, if enrolling more than one participant population, describe the total enrollment for each. Tip: consider attrition and the number of participants who may fail screening. Use of a range may provide flexibility. Note that the range must be justified in the **Justification of Sample Size section below.**]

The total number of subjects that will be enrolled into the intervention will be 150. It is estimated that we will screen 2,000 participants to achieve this recruitment goal. Since the initial contact is via an online link, there will be many incomplete responses driving up the number of screened-out participants.

Justification of Sample Size: [For qualitative and pilot studies, describe how the proposed sample size is appropriate for achieving the anticipated results. For quantitative studies, provide a power analysis that includes effect size, power and level of significance with references for how the sample size was determined. Explain the rate of attrition and possible number who fail the screening, with references as appropriate.]

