The number of subjects to be recruited for this study is approximately 150. Assuming 15% attrition, 127 participants will complete the study. With $\alpha=0.05$ and $N=127$, and assuming $SD=6.0\%$ (based 6-month weight loss in the online condition of our recent weight loss trial), we will have 80% power to detect mean 6-month weight change of $\pm 1.5\%$ or greater using a two-sided one-sample t-test.

Enrollment of UConn Students and/or Employees: [Will UConn students be enrolled? If so, describe if these students include those who any key research personnel teaches, or for whom any key research personnel has responsibility. Will UConn employees be enrolled? If so, describe if these employees report to any key personnel. For each group, explain why this population is *necessary* to the study. Tip: convenience is not sufficient justification.]

UConn students and employees may be enrolled if they meet eligibility requirements and are interested in completing the study. Students and employees directly reporting to key personnel on this project will be excluded from participation.

Enrollment of Key Personnel, Spouses or Dependents/Relatives: Will study key personnel, spouses of key personnel, or dependents/relatives of any key personnel be enrolled in the study? If so, describe and provide justification.

No.

For EACH Participant Population Describe Screening Procedures, if applicable: [Describe when participants will be screened and how this will occur. Include copies of all screening forms and related documents. Describe procedures to notify participants of the screening result, if applicable. Provide a copy of the screening instrument.]

We are recruiting overweight and obese individuals of all races and ethnicities, income, and education levels between the ages of 18 and 75 years in the United States. Participants must have regular home Wi-Fi connectivity.

Anticipated Study Time Frame: [Describe the estimated time frame of the study from anticipated start to anticipated finish. If the study will occur in more than phase include these in the time frame. Use of a table is often helpful.]

Project Time Frame:

This study will last for approximately 1 year and will include the following components:

Month	Nov	Dec	Jan	Feb	Mar	Apr	May	Jun	Jul	Aug	Sep	Oct
Start-up	X	X										
Recruitment			X	X	X							
Intervention					X	X	X	X	X	X	X	X
Follow-ups								X	X	X	X	X
Data manag	X	X	X	X	X	X	X	X	X	X	X	X

ement and analyse s											
Final Report											X

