[Describe the conditions under which participants may be removed from the study, i.e., noncompliance with study rules, study termination, etc.]

Participants will be withdrawn from the study if: they drop from participation, do not complete all screening procedures or post inappropriate content on the social network. Participants reporting that they would like to withdraw from the study will be given the option to: 1) withdraw from all intervention-related activity and contacts, but still complete the final assessment or 2) withdraw from the study completely with no additional study contact. If a participant becomes pregnant during the study, they will be withdrawn from the intervention, but will be given the option to still complete the follow-up assessments.

Potential Harms/Risks and Inconveniences: [Describe the potential risks to participants (and secondary participants, if applicable) and *steps taken to minimize risks* for each participant population. Assess the likelihood of the risk occurring and, if it were to occur, the seriousness to the participant. Types of risks to consider include, but are not limited to: physical, psychological, social, legal, employment, and financial.]

Possible risks for being in this study includes: Injury while exercising, breach of confidential information, and discomfort completing measures. The attempt to avoid risks to participants will be addressed by: suggesting moderate intensity exercise to avoid discomfort, pain, or injury. Participants reporting discomfort will be referred to their PCP. Injuries are unlikely to occur since we screen out medical conditions that could make someone prone to injury and we only suggest moderate activity. Moderate-level physical activity is 3.0 - <6.0 METs, which includes activities such as walking briskly (2.5 to 4 mph), playing doubles tennis, or raking. We also provide

participants with information on exertion level and remind them to seek medical attention if there is pain. Tracking data will be stored electronically in REDCap, a network secure data entry program; any data on paper will be stored in a locked file cabinet; and participants will be informed that they may withdraw from the study at any time if they feel discomfort with any of the study procedures.

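### The withdrawal rule offers early leavers only the final assessment, and offers no follow-up to those taken off the study, so obtainable 3-month and some 6-month weights may go uncollected

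*Protocol*

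**What the plan says.** The study aims in the protocol name both time points: "Preliminary outcome is defined as weight change from baseline to 3 and 6-months". The Data Analysis section and the SAP (Aim 1) calculate percent weight change to each. The Follow-ups section places the surveys in weeks 13 and 27 and also collects weight at 3 and 6 months.

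The paragraph on removal of participants, at the end of the Inclusion/Exclusion Criteria section, contains three rules:

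- **Withdrawal from the study.** This applies if "they drop from participation, do not complete all screening procedures or post inappropriate content on the social network". No later assessment is offered.
- **Participants who ask to leave.** Option 1 is to "withdraw from all intervention-related activity and contacts, but still complete the final assessment". Option 2 is to leave entirely, with no more contact.
- **Participants who become pregnant.** Here "they will be withdrawn from the intervention, but will be given the option to still complete the follow-up assessments".

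A missing 6-month weight is replaced by the baseline weight (baseline observation carried forward, BOCF), with a complete-case estimate second. Neither document gives a rule for a missing 3-month weight.

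**The concern.** Stopping the program and stopping measurement are separate events. The protocol separates them fully for pregnancy, partly under option 1, and not at all for those withdrawn from the study.

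A participant who takes option 1 in, say, week 5 has agreed to go on giving data, but the 3-month assessment is not among the things offered. A participant removed for content is offered nothing further. In both cases the weight could probably be had: the participant has a study scale at home, and the protocol already describes sending a photograph of its display through REDCap, although only for scales that fail to pair.

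Two things are at stake. The first is bias in the mean weight change, chiefly at 3 months, where there is no missing-data rule. The second is the engagement analyses, which relate program use to weight loss at 3 and 6 months. Early leavers have had less time to use the program, so their absence removes outcomes from one end of the exposure range.

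**Working it through.** **1. The plan's own figure.** The protocol states that "The total number of subjects that will be enrolled into the intervention will be 150" and "Assuming 15% attrition, 127 participants will complete the study". The check is 150 × 0.85 = 127.5, taken as 127, which leaves 150 − 127 = 23 planned losses. The sample size section uses a two-sided α of 0.05, SD 6.0% and a mean change of 1.5%. The noncentrality is (1.5/6.0) × √127 = 2.82. Power from the noncentral t distribution is 79.8% (80.4% by normal approximation), so the stated 80% reproduces. It already allows for 15% attrition.

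**2. What each rule asks for.**

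| Participant | 3-month weight | 6-month weight |
|---|---|---|
| Stays in the program | requested | requested |
| Option 1, before week 13 | not offered | requested |
| Option 2 | none, own choice | none, own choice |
| Becomes pregnant | offered, if still due | offered |
| Removed for content | not offered | not offered |
| Drops from participation | unclear (undefined) | unclear (undefined) |

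Incomplete screening comes before enrolment and costs no follow-up weight. The avoidable losses are therefore the 3-month weight under option 1, any weight still due after removal for content, and whatever the undefined clause covers.

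**3. Size of the bias (illustration).** Let m be the share of 150 without a weight, c the mean loss in those measured and d the true mean loss in those missing. The all-enrolled mean is (1 − m)c + md. Then:

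- complete-case error = c − [(1 − m)c + md] = m(c − d)
- BOCF error = (1 − m)c − [(1 − m)c + md] = −md

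Assume c = 5%, and d = 1.5% (a smaller loss) or d = −1% (a gain). None of these values is in the documents.

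| | d = 1.5% | d = −1% |
|---|---|---|
| m = 15%: all-enrolled mean | 4.48% | 4.10% |
| Complete case (5.00%), error | +0.53 | +0.90 |
| BOCF (4.25%), error | −0.23 | +0.15 |
| Half retrieved: complete-case error | +0.24 | +0.41 |
| Half retrieved: BOCF error | −0.11 | +0.08 |
| Per person missing (m = 1/150): complete case | +0.023 | +0.040 |
| Per person missing: BOCF | −0.010 | +0.007 |

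The 15% rows treat all planned attrition as missing. The share due to this rule is unknown, so the last two rows are the safer guide. The retrieved half is assumed to be representative of those missing.

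**The case against.** The strongest reply is that little is lost at the powered time point. Option 1 keeps the 6-month weight, option 2 is the participant's own decision, and at 6 months only content removals and an unclear clause remain. That stands, and it limits the 6-month part of the point.

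The pregnancy rule also covers a different group from option 1. The difference is an inconsistency of wording that needs reconciling, not a strict contradiction. Weights might still arrive through the program provider, which collects scale data continuously. The protocol does not say whether this goes on after withdrawal from all intervention activity, so it can be neither counted on nor excluded.

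A reader might infer four stronger things, none of which the documents support:

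- **A head count taken from the 23 planned losses.** Those 23 do not complete the study. An option 1 participant who gives the final weight belongs among the 127, so no share of the 23 measures the 3-month loss.
- **Low users are struck off.** No app-use or attendance threshold for removal appears, and the Follow-ups section attaches no engagement condition to the surveys. Low users who do not ask to leave are, on the text, still followed. Dropping from participation may simply mean dropping out.
- **The sample size is wrong.** It is not; the power reproduces with attrition allowed for.
- **Study withdrawal for content is redundant because moderators can ban.** Banning is mentioned only for trolling, and workshops are shared too. Who stays in the program is a separate matter from who is measured.

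**Conclusion.** The point holds as an avoidable source of missing outcome data. Read as written, option 1 omits the 3-month assessment for people who have agreed to remain in follow-up. Those taken off the study for content, or under the undefined clause on dropping from participation, are offered no follow-up, and their missing 6-month weight becomes no change.

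The number affected cannot be derived. Under the stated assumptions, each lost weight moves a complete-case mean by 0.02 to 0.04 percentage points and a BOCF mean by about 0.01, against a detectable change of 1.5%. The effect is modest, and falls mainly on the 3-month result and the engagement analyses. The conclusion assumes that staff apply the paragraph literally and that the provider's scale feed does not fill the gap. The change is worth making because it is cheap, not because the main 6-month test is at risk.

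**What to change.** In the paragraph on removal from the study, keep the first half of option 1 and replace the single final assessment with the remaining follow-up assessments, meaning the 3-month and 6-month weight and survey. Offer the same follow-ups to anyone removed for content or who drops from participation, unless that person chooses complete withdrawal. Define dropping from participation, and reconcile it with option 1 and with the pregnancy rule so that all three use the same terms for what is stopped and what is still collected. Who is removed from the program or the Facebook group remains for the sponsor to decide; this change concerns outcome collection only.

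The cost is a short amendment and an edit to the information sheet. For each follow-up that would otherwise be missed, it adds at most one survey link, one weight request and the $50 payment already set for that survey.
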